7.2 Schedule of Events

The trial Schedule of Events is shown in **Table 4**.

Table 4. Schedule of Events (see also Table 3 for timing of outcome measures)

Task	Year					
	1	2	3	4	5	6
IRB approval	X					
Engaging patients and stakeholders	X	X	X	X	X	X
Refining the interventions and tailoring to CTS	X					
Training DCS' and CBDC Care Consultants	X					
Piloting the intervention and outcomes at CTSs	X					
Recruitment of participants		X	X			
Follow-up of participants		X	X	X	X	
Data collection, quality management and analysis		X	X	X	X	
Data analysis					X	X
Write papers and dissemination			X	X	X	X
Obtain claims data					X	
Conduct cost-effectiveness analysis					X	X
Write papers and dissemination			X	X	X	X
PCORI Peer-Review Process						X

8. STATISTICAL ANALYSIS, SAMPLE SIZE AND POWER CALCULATIONS

8.1 Design Overview

This section describes the general approach for the analysis of the primary, secondary and tertiary outcomes, including safety. The trial will be registered on clinicaltrials.gov before the first patient is enrolled and results will be reported within one year of obtaining the primary outcome on the last patient. Current versions of SAS and R will be used for all analyses.

8.2 Analysis of Primary, Secondary, and Tertiary Outcomes

8.2.1 Analysis of Primary Outcomes

All analyses will be according to intent-to-treat or as-randomized. The analysis of the two primary outcomes – NPI-Q Severity and MCSI scores – will be done using a constrained longitudinal repeated measures analysis²⁶ based on maximum likelihood methods adjusted for the stratified randomization by site. Treatment differences, averaged over all follow-up time points, will be summarized by least square means and 97.5% confidence intervals. Significance testing for each outcome will be done by the Hochberg procedure²⁷ using an overall type I error of 2.5% (2-sided) to control for the 3 pairwise comparisons, i.e., testing each outcome at 2.5% will maintain the overall type I error at 5% (2-sided). This analysis will be implemented as a mixed methods repeated measures (MMRM) model which uses all available records under the assumption that visit-specific data are missing at random (MAR). Inclusion of the baseline 3, 6, 12, and 18-month data as outcomes in the model will assist in meeting the MAR assumption. We will test for the treatment by time interaction at the 10% significance level. If significant, we will also report treatment differences at each time point. We will also

A PRAGMATIC TRIAL OF THE EFFECTIVENESS AND COST-EFFECTIVENESS OF DEMENTIA CARE/COMPARATIVE EFFECTIVENESS OF HEALTH SYSTEM-BASED VERSUS COMMUNITY-BASED DEMENTIA CARE

examine for treatment by site interactions, although there may not be power to detect them. Sensitivity analyses will investigate the MAR assumption, such as methods that jointly model missingness and outcome distributions (e.g., pattern mixture models).^{28,32}

We will conduct an exploratory analysis to test whether giving any intervention is superior to usual care if there is no significant difference between the two interventions, and if neither intervention is superior to usual care for either or both outcomes. We will test this hypothesis using the same longitudinal repeated measures analysis described for the primary outcomes at the 0.05 (2-sided) level of significance uncorrected for multiplicity. The difference between giving any intervention and usual care will be reported as least square means with 95% confidence intervals.

Heterogeneity of treatment effects (HTE) for the primary outcomes will be assessed in six key subgroups of participants: higher vs. lower patient function by FAQ, independent vs. dependent patient function by ADL, more vs less NPI-Q Severity, more vs less MCSI at baseline, spouse caregiver vs. other caregiver, and white non-Latino vs. nonwhite or Latino. These subgroup analyses are aimed at determining whether there is differential effectiveness of the interventions among patients with more and less severe disease, perhaps elucidating a preventive (if effect is greater among those with less severe disease) versus therapeutic (if effect is greater among those with more severe disease) effect. Similarly, the high vs low distress subgroup comparison will determine whether the intervention is more effective among those with more distress at baseline (a therapeutic benefit) versus less distress (a preventive benefit). Evidence of HTE will be based on tests of interaction within the longitudinal model structure described above. Because six tests of interaction will be conducted, we will use the Hochberg procedure to control for multiplicity using an overall type I error of 2.5% (2-sided) for each outcome; subgroup treatment differences will be reported using 99% confidence intervals.

Exploratory analyses to assess HTE for the primary outcomes will be also be conducted in demographic subgroups (e.g., age, race and ethnicity) as well as the effects of the COVID-19 pandemic and not adjusted for multiplicity.

8.2.2 Analysis of Secondary Outcomes

The analysis of the continuous secondary outcomes – NPI-Q Distress, caregiver depression (PHQ-8), Caregiver self-efficacy– will be analyzed like the primary outcomes. The Hochberg procedure will be used to control for the testing of each secondary outcome using an overall type I error of 5% (2-sided); treatment differences will be reported using 95% confidence intervals.

8.2.3 Analysis of Tertiary Outcomes

The analysis of tertiary outcomes will be considered exploratory and, thus, no control for multiplicity will be done. Continuous outcomes will be analyzed by longitudinal methods, time to event data by survival methods and count data by Poisson, Negative Binomial, hurdle models or rank based methods depending on the distribution of the counts. Time spent at home is calculated as 540 minus (1) the number of days in a health care facility, including hospital, nursing home, acute rehabilitation, and inpatient hospice, and (2) the number of days not alive. The analytical approach will depend on the distribution of the outcome (e.g., skewed distributions will require rank-based methods.)

8.2.4 Missing Data

Several strategies will be implemented to address the issue of missing data during this study. Prevention is the most obvious and effective manner to control bias and loss of power from missing data.²⁹ (see section 9.1.7 “Data Quality Control” for a discussion of our plans to minimize missing data and other errors during data

A PRAGMATIC TRIAL OF THE EFFECTIVENESS AND COST-EFFECTIVENESS OF DEMENTIA CARE/COMPARATIVE EFFECTIVENESS OF HEALTH SYSTEM-BASED VERSUS COMMUNITY-BASED DEMENTIA CARE

collection). This protocol will follow the intent-to-treat principle, requiring follow-up of all participants randomized regardless of the actual treatment received.³⁰ The primary source of missing data will result from death since we expect relatively few dropouts (< 10%). Whenever a participant drops out of the study, we will document the specific reason for dropout, who decided that the participant would drop out, and whether the dropout involves some or all types of participation. For example, some participants may drop out of the patient/caregiver-reported outcomes but permit use of claims data to determine some secondary and tertiary outcomes.

The follow-up period of 18 months was set to capture the time period during which treatment benefits would be maximized while minimizing the impact of deaths. Also, the timing and frequency of follow-up assessments at 3, 6, 12, and 18 months was designed to minimize missing primary outcome data on participants by having measurements at early time points.

Because the study population has dementia, the primary source of data collection (including primary and all secondary outcomes) will be from caregivers. To minimize missing data, all follow-up data will be collected by telephone, making it much easier, compared to in person visits, for participants (and caregivers) to complete the outcomes assessments. Because most instruments, including the two primary outcome measures are self-administered, we can also offer the options of collecting these data by fax, secure website, or secure email, which will also reduce the likelihood of missing data. We will also employ a risk-based approach to trial monitoring with timely data entry combined with weekly missing data reports that will trigger protocols for tracking and obtaining missing data items or outcome assessments³¹ data.

Despite these prevention efforts, it is reasonable to assume missing data will occur. Our primary analysis is valid under the assumption that missing data is missing at random (MAR). Sensitivity analyses will investigate the MAR assumption, such as methods that jointly model missingness and outcome distributions (e.g., pattern mixture models).^{29,31} The results of these techniques to account for missing data will be incorporated into the interpretation of findings and conclusions of the study.

8.3 Sample Size

8.3.1 Primary Outcomes

The assumptions used to determine sample size for testing differences among the three treatment arms for the two primary outcomes were: 1) type I error $0.05/6 = 0.0083$ adjusted for 3 treatment comparisons (HSDC vs. CBDC, HSDC vs. UC and CBDC vs. UC) times 2 primary outcomes, 2) standard deviation (SD) for NPI-Q severity of 6.5 units and SD for MCSI of 6.7 units, 3) treatment difference for HSDC vs. CBDC of 1.5 units, 4) treatment difference for HSDC and CBDC vs. UC = 3 and 5) lost to follow up over 18 months because of death and dropout of 25%. The detectable treatment difference of 1.5 units for HSDC vs. CBDC is based on data reported in the literature suggesting a minimally clinical important difference (MCID) ranging from 2.8 to 4.0.⁶ Given that both intervention arms will be receiving an intervention, we reduced the detectable difference in half to 1.5. Data from two studies^{32,33} indicate that the expected benefit between HSDC and UC would be 3.2 units for NPI-Q Severity score. Based on these data we used a difference of 3 units for comparisons with UC. The estimates of the standard deviations (SD) for the 18-month NPI-Q Severity score and MCSI are 6.5 and 6.7, respectively, based on UCLA pilot data. An 18-month censoring rate of 25% was assumed because of death (15%) and dropout (10%). The death rate was taken from fee-for-service claims data on 274 UCLA patients with a mean survival time of 1.5 years.

Sample size was first determined for the comparison between HSDC and CBDC because the effect size is smaller. The goal was to achieve at least 90% overall power for testing both outcomes. Testing each outcome at 95% power with a sample size of 1000 subjects per treatment group (adjusted for censoring) gives at least 90% overall power for testing both outcomes. Given these sample sizes, the sample size is 150 (for UC

A PRAGMATIC TRIAL OF THE EFFECTIVENESS AND COST-EFFECTIVENESS OF DEMENTIA CARE/COMPARATIVE EFFECTIVENESS OF HEALTH SYSTEM-BASED VERSUS COMMUNITY-BASED DEMENTIA CARE

adjusted for censoring) for comparisons with the two interventions giving an overall power of at least 90%. For conservatism, we assumed the same effect size for both interventions compared with UC even though we hypothesize that HSDC will be superior to CBDC. The total sample size for the trial is 2150 individuals (adjusted for censoring).

Table 5: Power and Sample Size for the Two Primary Outcomes

Comparison	Difference to be detected	Power for MCSI	Power for NPI-Q Severity	Overall Power	Adjusted Sample Sizes
HSDC vs. CBDC	1.5	95%	95%	90%	1000 per group
HSDC or CBDC vs. UC	3.0	95%	95%	90%	1000 HSDC and CBDC vs. 150 UC

The inflation of sample size for censoring due to deaths and losses is conservative because the data will be analyzed using longitudinal methods under the MAR assumption that include all available data on each participant. Considering the first patient follow-up for the two primary outcomes is at 3 months, the effective censoring rate for analytical purposes is approximately 5% for the primary analysis (i.e., those without any primary outcome follow-up data).

Heterogeneity of treatment effects (HTE) for the two primary outcomes will be assessed in six subgroups of participants: high vs. low patient function by FAQ, high vs. low patient function by ADL, high vs. low NPI-Q Severity, high vs low MCSI at baseline, spouse caregiver vs. other caregiver, and white non-Latino vs. nonwhite or Latino. The study will have approximately 90% power to detect interactions (differences in treatment effects between subgroup categories) of about 3 units for both NPI-Q severity and MCSI for the HSDC vs. CBDC comparisons. Interactions on the order of 6 units can be detected with approximately 90% power for comparisons of HSBC and CBDC with UC for the two primary outcomes. These detectable interactions assume a conservative Bonferroni adjusted type I error of $0.05/(6 \times 3 \times 2) = 0.0014$ to control for multiplicity. (In the analysis, we will conduct one global test of interaction per subgroup for 6 subgroups). Using an anchor-based approach that compares changes in NPI-Q measures with other clinical measures, the MCID for the severity scale is 3.2.⁶ Hence, based on this range of MCID, the study will have adequate power to detect clinically meaningful differences in subgroups for comparisons between the two interventions. However, only large interactions can be detected for the comparisons with UC because of the smaller sample size in this arm. Although equal subgroup sample sizes were assumed in the calculations, power will not be greatly affected if the imbalance in subgroup sample sizes is not more extreme than a ratio of 2:1.

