6.1.1 Primary Outcomes

Because of the importance of both the patient and caregiver in dementia care, the primary outcome measures will be both the Severity scale of the Neuropsychiatric Inventory Questionnaire (NPI-Q)⁵ and the Modified Caregiver Strain Index (MCSI). The NPI-Q Severity is a validated survey that assesses the caregiver's perception of the severity of 12 dementia-related psychiatric and behavioral symptoms. NPI-Q Severity score ranges from 0-36 with higher scores indicating more severe symptoms. In a nursing home population, the minimal clinically important difference (MCID) was determined to be 2.8-3.2 points.⁶ The MCSI⁷ is a 13-item validated tool used to assess severity of caregiver strain. The index targets financial, physical, psychological, and social aspects of strain and is scored from 0 to 26 with higher scores indicating greater levels of strain. The MCID is 1.5-2.3 points.

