6.1.2 Secondary Outcomes

Secondary outcomes include caregiver self-efficacy, distress in response to dementia-related psychiatric and behavioral symptoms, and depressive symptoms.

A PRAGMATIC TRIAL OF THE EFFECTIVENESS AND COST-EFFECTIVENESS OF DEMENTIA CARE/COMPARATIVE EFFECTIVENESS OF HEALTH SYSTEM-BASED VERSUS COMMUNITY-BASED DEMENTIA CARE

The NPI-Q Distress scale is a validated survey that assesses the level of distress experienced by the caregiver in response to dementia-related psychiatric and behavioral symptoms. NPI-Q Distress score ranges from 0-60 with higher scores indicating more severe distress. In a nursing home population, the MCID was determined to be 3.1-4.0 points for distress.⁶

Caregiver Self-Efficacy is measured with a 4-item self-efficacy scale assessing the caregiver's ability to manage dementia-related problems and ability to access help, including community resources.

Patient Health Questionnaire-8 (PHQ-8)⁸ is a shortened version of the PHQ-9 (item 9 is omitted) that is often used when the instrument is administered by telephone and intervention cannot be adequately provided. The PHQ-9 is 9-item validated tool used to assess depressive symptoms in the caregiver using the DSM-IV criteria for major depression and is scored from 0-27 with scores >10 indicating moderate symptoms and scores >20 indicating severe depressive symptoms. Because of the infrequency of positive responses to item-9, its deletion has minimal effect on scoring and identical scoring thresholds for depression severity can be used.⁹

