## **6. SAMPLE SIZE**

### **6.1 Primary Outcomes**

The assumptions used to determine sample size for testing differences among the three treatment arms for the two primary outcomes were: 1) type I error  $0.05/6 = 0.0083$  adjusted for 3 treatment comparisons (HSDC vs. CBDC, HSDC vs. UC and CBDC vs. UC) times 2 primary outcomes, 2) standard deviation (SD) for NPI-Q severity of 6.5 units and SD for MCSI of 6.7 units, 3) treatment difference for HSDC vs. CBDC of 1.5 units, 4) treatment difference for HSDC and CBDC vs. UC = 3, and 5) lost to follow up over 18 months because of death and dropout of 25%. The detectable treatment difference of 1.5 units for HSDC vs. CBDC is based on data reported in the literature suggesting a minimally clinical important difference (MCID) ranging from 2.8 to 4.0 (Mao et al., 2015). Given that both intervention arms will be receiving an intervention, we reduced the detectable difference in half to 1.5. Data from two studies (Callahan et al., 2006; [name], 2016) indicate that the expected benefit between HSDC and UC would be 3.2 units for NPI-Q Severity score. Based on these data we used a difference of 3 units for comparisons with UC. The estimates of the standard deviations (SD) for the 18-month NPI-Q Severity score and MCSI are 6.5 and 6.7, respectively, based on UCLA pilot data. An 18-month censoring rate of 25% was assumed because of death (15%) and dropout (10%). The

death rate was taken from fee-for-service claims data on 274 UCLA patients with a mean survival time of 1.5 years.

Sample size was first determined for the comparison between HSDC and CBDC because the effect size is smaller. The goal was to achieve at least 90% overall power for testing both outcomes. Testing each outcome at 95% power with a sample size of 1000 subjects per treatment group (adjusted for censoring) gives at least 90% overall power for testing both outcomes. Given these sample sizes, the sample size is 150 (for UC adjusted for censoring) for comparisons with the two interventions giving an overall power of at least 90%. For conservatism, we assumed the same effect size for both interventions compared with UC even though we hypothesize that HSDC will be superior to CBDC. The total sample size for the trial is 2150 individuals (adjusted for censoring).

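### Does using an NPI-Q-based 3-unit difference for MCSI undermine the stated 95% power against usual care?

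*Protocol*

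**What the plan says.** Protocol 8.3.1 and SAP 6.1 set two design differences and apply each to both NPI-Q Severity and MCSI.

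- **HSDC versus CBDC, 1.5 units.** This is described as about half of a value drawn from "data reported in the literature suggesting a minimally clinical important difference (MCID) ranging from 2.8 to 4.0".
- **Either intervention versus usual care, 3 units.** Two studies are said to imply a 3.2-unit benefit on NPI-Q Severity, and then: "Based on these data we used a difference of 3 units for comparisons with UC".

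The other inputs are "type I error $0.05/6 = 0.0083$ adjusted for 3 treatment comparisons" and two outcomes, "standard deviation (SD) for NPI-Q severity of 6.5 units and SD for MCSI of 6.7 units", and 25% loss by 18 months. Protocol Table 5 (SAP Table 2) reports 95% power for each outcome in both types of comparison.

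The scale-specific values are elsewhere in the protocol. Section 6.1.1 gives 2.8-3.2 for NPI-Q Severity and, for MCSI, "The MCID is 1.5-2.3 points". Section 6.1.2 says of NPI-Q Distress, a secondary outcome, that "the MCID was determined to be 3.1-4.0 points for distress". On subgroups, Protocol 8.3.1 cites 3.2 as the value for the severity scale and continues: "Hence, based on this range of MCID, the study will have adequate power to detect clinically meaningful differences in subgroups". That sentence concerns HSDC versus CBDC only.

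**The concern.** The range of 2.8 to 4.0 joins the NPI-Q Severity and NPI-Q Distress ranges and contains no MCSI value. The 3.2-unit expected benefit is also an NPI-Q Severity figure. Only the SD of 6.7 is specific to MCSI. Three units is 3.0/2.3 = 1.3 to 3.0/1.5 = 2 times the MCSI difference that the protocol itself calls important, and the SAP never states that MCSI value.

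Usual care is the smallest arm, with 150 of 2150 dyads. If the trial had little power there for an important MCSI effect, a null MCSI result could be misread as evidence of no such effect because the table shows 95%. The subgroup sentence seems to carry the same fault, since a 3-unit MCSI interaction is above the whole MCSI range.

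**Working it through.** **Inputs (Protocol 8.3.1).** Alpha is 0.05/6 = 0.0083. It is taken as two-sided, because Protocol 8.2.1 tests "using an overall type I error of 2.5% (2-sided) to control for the 3 pairwise comparisons"; the critical value is 2.638. SDs are 6.7 (MCSI) and 6.5 (NPI-Q Severity). After 25% loss, 1000 becomes 750 and 150 becomes 112.5.

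**1. Reproduce the table.** Power is approximately Φ(d/SE − 2.638), with SE = SD × √(1/n₁ + 1/n₂).

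- MCSI versus usual care: SE = 6.7 × √(1/750 + 1/112.5) = 0.677. At d = 3.0, 3.0/0.677 = 4.429 and power is 96.3%.
- NPI-Q Severity versus usual care: SE = 0.657. At 3.0, power is 97.3%.
- MCSI, HSDC versus CBDC: SE = 6.7 × √(2/750) = 0.346. At 1.5, power is 95.5%.

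All three agree with the stated 95%.

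**2. Same calculation at the MCSI range, versus usual care.**

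| Loss assumed | n | d = 1.5 | d = 2.3 |
|---|---|---|---|
| 25% | 750 vs 112.5 | 33.6% | 77.5% |
| 5% (the plan's effective rate) | 950 vs 142.5 | 44.2% | 88.2% |

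On the 25% basis, a 97.5% interval has half-width 2.241 × 0.677 = 1.52.

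**3. Compare with the planned test.** Step 2 is a contrast of single 18-month values. Protocol 8.2.1 and SAP 9.3 instead estimate the mean difference over the 3-, 6-, 12- and 18-month visits, in a constrained model that includes baseline as an outcome. With complete visits, the variance is multiplied by

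f = (1 + 3r)/4 − b²,

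where r is the correlation among follow-ups and b the correlation of each follow-up with baseline. The documents give neither, so the values below are assumptions. They keep SD 6.7, 750 versus 112.5 at every visit, and alpha 0.05/6.

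| Assumed correlation | f | SE = 0.677 × √f | Power at 1.5 | Power at 2.3 | 97.5% half-width |
|---|---|---|---|---|---|
| r = b = 0.375 (largest f when r = b) | 0.391 | 0.423 | 81.7% | 99.7% | 0.95 |
| r = b = 0.5 | 0.375 | 0.415 | 83.6% | 99.8% | 0.93 |
| r = b = 0.7 | 0.285 | 0.362 | 93.4% | >99.9% | 0.81 |
| r = 0.8, b = 0.5 (unfavourable) | 0.600 | 0.525 | 58.7% | 96.0% | 1.18 |

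When r = b, f = (1 + 3r)/4 − r² peaks at r = 0.375. The first row is therefore the worst case under equal correlation.

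**4. Subgroups, HSDC versus CBDC.** With equal subgroups, SE = 6.7 × √(4/375) = 0.692. The stated alpha is 0.05/36 = 0.0014, with critical value 3.197. A 3-unit MCSI interaction has 87% power (90% for NPI-Q Severity with SD 6.5), in line with the plan's approximate 90%. At 2.3 and 1.5 units MCSI power is 55% and 15%, again for a single visit without baseline.

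**The case for a change.** The strongest case for acting is that Table 5 gives MCSI power at a difference justified only on another scale, while the protocol holds an MCSI value and does not use it. Powering on expected benefit rather than on a minimal important difference is legitimate, but no expected MCSI benefit against usual care is given. On the same basis as the table's 95%, the range is 34% to 78%, and the plan's 5% effective loss only raises it to 44% to 88%. The gain from the longitudinal model rests on correlations that the documents do not report. A correction would need only a few words.

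The missing MCSI rationale stands, and so does the merging of two NPI-Q ranges. The subgroup sentence is loose for MCSI, although the text just before it names the severity scale, and the text after it warns that only large interactions can be detected against usual care.

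The practical consequence does not stand. Entering 34% to 78% in the table as the MCSI power would describe a test that the trial will not run. The 1.52 half-width likewise belongs to a single-visit contrast. Even in the unfavourable scenario the planned interval is narrower, at 1.18, so a null result against usual care could not be called inconclusive in advance.

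**Conclusion.** No change is needed. The 3-unit figure comes from NPI-Q Severity and has no stated MCSI basis, which is a gap in documentation. It is not an error in the power: the design delivers the 95% that it claims at 3.0 units. The comparison that set the sample size, HSDC versus CBDC at 1.5 units, sits at the lower end of the MCSI range and has 95.5% power.

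At 1.5 to 2.3 MCSI units against usual care, the planned analysis probably has considerably more power than the simple calculation shows. The figures are about 82% and 99.7% at worst under equal correlation, and 59% and 96% under the unfavourable pattern. They assume complete visits in 750 and 112.5 dyads, an SD of 6.7 and correlations that the documents do not supply.

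SAP section 8 records that the primary database was frozen on 4/9/2024, so no sample-size decision remains open. The plan already reports 97.5% intervals for the averaged difference, and a reader can set these against the 1.5 to 2.3 points in Protocol 6.1.1. Rewording the justification would leave the model, tests, intervals and conclusions as they are.

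### Adequate power for HSDC versus CBDC subgroup differences is claimed for both primary outcomes, but only the NPI-Q Severity MCID supports it; at the MCSI's own MCID, interaction power is about 15-55%

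*Protocol*

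**What the plan says.** Protocol 8.3.1, repeated in SAP 6.1, plans tests of effect heterogeneity in six subgroup factors for both primary outcomes. For HSDC versus CBDC it states "approximately 90% power to detect interactions (differences in treatment effects between subgroup categories) of about 3 units for both NPI-Q severity and MCSI". On the error level it says "These detectable interactions assume a conservative Bonferroni adjusted type I error of" 0.05/(6 x 3 x 2) = 0.0014. It then quotes 3.2 as the MCID of the NPI-Q severity scale and concludes that "the study will have adequate power to detect clinically meaningful differences in subgroups for comparisons between the two interventions". The caution that follows, that only large interactions can be found, is confined to comparisons with usual care.

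Two other statements bear on this:

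- Protocol 6.1.1 says of the MCSI: "The MCID is 1.5-2.3 points". The same section gives 2.8-3.2 for NPI-Q Severity. The SAP's description of the MCSI (section 5.2) gives no MCID.
- Earlier in Protocol 8.3.1, on the overall HSDC versus CBDC effect: "Given that both intervention arms will be receiving an intervention, we reduced the detectable difference in half to 1.5".

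**The concern.** The detectability statement names both outcomes, but the yardstick that turns it into adequacy belongs to one of them. A 3-unit interaction is about the size of the NPI-Q Severity MCID. It lies above the whole MCID range that the Protocol gives for the MCSI.

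There is also an unexplained change of scale within the section. For the overall comparison of the two programs, the plan sizes on half the MCID because both arms are treated. For subgroup differences between the same two programs, it goes back to the full MCID and gives no reason. If the overall effect is 1.5 and the subgroups are equal in size, a 3-unit interaction means, for example, an effect of 3.0 in one subgroup and 0 in the other. Smaller interactions are at least as plausible.

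The heterogeneity analysis is formal and controlled for multiplicity, and it is meant to separate preventive from therapeutic benefit. With a blanket statement of adequate power on file, a non-significant interaction could be taken as evidence that the programs differ equally across subgroups. For the MCSI that inference would have little support.

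**Working it through.** **Inputs, all from Protocol 8.3.1 unless noted**

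- "standard deviation (SD) for NPI-Q severity of 6.5 units and SD for MCSI of 6.7 units".
- 1000 randomised per intervention arm and 25% loss (15% death, 10% dropout), so 1000 x 0.75 = 750 per arm.
- Equal subgroups, so 375 per arm-by-subgroup cell.
- Alpha = 0.05/36 = 0.00139, taken as two-sided like the rest of the plan; z = 3.197.
- MCSI MCID 1.5-2.3 and NPI-Q Severity MCID 2.8-3.2 (Protocol 6.1.1).

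**Method.** An interaction is a difference of two treatment differences, so it has four cells:

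SE = SD x sqrt(4/375), and power = Phi(d/SE - 3.197).

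- NPI-Q Severity: SE = 6.5 x 0.1033 = 0.671.
- MCSI: SE = 6.7 x 0.1033 = 0.692.

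**Reproducing the plan's figure (d = 3)**

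- NPI-Q Severity: 3/0.671 = 4.469; Phi(4.469 - 3.197) = Phi(1.272) = 89.8%.
- MCSI: 3/0.692 = 4.335; Phi(1.138) = 87.3%.

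Both fit the plan's rounded statement. With 950 or 1000 per arm the result would be 95-98%, so 750 per arm is evidently the basis used.

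**Same method at other interaction sizes**

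| Interaction (units) | NPI-Q Severity | MCSI |
|---|---|---|
| 1.5 (MCSI MCID, lower end; also the overall HSDC-CBDC target) | 16.8% | 15.2% |
| 2.3 (MCSI MCID, upper end) | 59.1% | 55.0% |
| 2.8 (NPI-Q MCID, lower end) | 83.5% | 80.2% |
| 3.0 | 89.8% | 87.3% |
| 3.2 (NPI-Q MCID cited) | 94.2% | 92.3% |

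Worked MCSI entries: 1.5/0.692 = 2.168 and Phi(-1.029) = 15.2%; 2.3/0.692 = 3.324 and Phi(0.127) = 55.0%.

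**Sensitivity to less strict inputs.** The planned analysis applies Hochberg over six tests at 2.5% per outcome, whose smallest step is 0.025/6 = 0.0042 (z = 2.865). The plan also expects only about 5% of dyads to have no follow-up data, which leaves about 950 per arm.

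| Basis (equal subgroups, single contrast) | NPI-Q at 1.5 | MCSI at 1.5 | MCSI at 2.3 |
|---|---|---|---|
| 950 per arm, alpha 0.0014 | 24.8% | 22.4% | 70.7% |
| 750 per arm, alpha 0.025/6 | 26.4% | 24.3% | 67.7% |
| 950 per arm, alpha 0.025/6 | 36.3% | 33.5% | 80.9% |

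The last column uses the same formula. At 750, Phi(3.324 - 2.865) = 67.7%. At 950, SE = 6.7 x sqrt(8/950) = 0.615 and Phi(3.741 - 2.865) = 80.9%.

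The plan will in fact run one global test per factor across three arms (2 df). At 0.025/6, assuming the usual-care subgroup contrast lies midway between the two programs, its power at 1.5 units is 17-19% with 750 per arm and 24-27% with 950.

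**Sensitivity to subgroup split.** SAP Appendix A cuts FAQ, NPI-Q Severity and MCSI near the upper tertile (65.73%, 66.21%, 66.50%), which is roughly 2:1. At 750 per arm and alpha 0.0014, power at 3 units then falls to 84.5% (NPI-Q) and 81.3% (MCSI), and at 1.5 units to 13.8% and 12.4%.

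**The case against.** The strongest reply is that nothing is miscalculated. The stated power is right. The plan discloses the detectable size, the alpha and the MCID it uses, and at that MCID power exceeds 90% on both scales. All of that stands. The fault is in the conclusion drawn, and it concerns the MCSI most.

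A reader might infer that the plan redefined the MCID as 1.5 for this pair of arms and so contradicts itself on NPI-Q Severity. The documents do not support that. What Protocol 8.3.1 halves is the sizing target for the overall effect. It leaves the MCID alone and sets no target for an interaction. Applying 1.5 to an NPI-Q interaction extends the plan's reasoning.

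A reader might also take 15-17% as the power of the analysis that will be run. It is the conservative planning figure. Less strict levels and lower loss raise it, and averaging four follow-up visits may reduce the effective SD. The documents give no figure for that reduction. If it were 40% (an assumption), with 950 per arm and a single contrast at 0.025/6, power at 1.5 would be 90.8% for NPI-Q Severity and 88.5% for MCSI. So it cannot be said that no scenario reaches 90%. With a 20% reduction (also an assumption), 950 per arm and alpha 0.0014, MCSI power at 2.3 would be 93%. The adequacy sentence, however, rests on none of these inputs.

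Finally, the plan already reports subgroup treatment differences with 99% intervals, and nowhere says that a non-significant interaction will be read as equal effects. Both are true and limit the harm. The 99% intervals describe each subgroup separately and do not give the uncertainty of the contrast between them.

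**Conclusion.** The claim of adequate power is not supported as written for both primary outcomes. For the MCSI, the Protocol's own MCID of 1.5-2.3 gives about 15-55% interaction power on the inputs behind the plan's 90% figure. This needs no argument about halving. For NPI-Q Severity the claim holds near the full MCID (about 90% at 3.0 and 94% at 3.2). It does not extend to 1.5 units, where power is about 17%, and the plan does not explain why the full MCID applies here when half of it was used for the overall comparison.

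These results assume a two-sided 0.0014 level, 750 evaluable per arm, equal subgroups and single-time-point SDs. Relaxing alpha and loss gives about 24-36% at 1.5 for a single contrast. A smaller effective SD would raise it further by an amount the documents do not let one compute. The point corrects a stated property of the design; no estimate or test changes.

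**What to change.** In Protocol 8.3.1 and SAP 6.1, replace the adequacy sentence with:

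*For HSDC vs. CBDC the study has about 90% power for interactions of about 3 units, which is near the NPI-Q Severity MCID but above the MCSI MCID of 1.5-2.3 and twice the 1.5-unit overall target; on the same conservative inputs, power is about 15-17% at 1.5 units and about 55-59% at 2.3 units.*

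In Protocol 8.2.1 and SAP 9.3.1, add two commitments:

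1. Report the HSDC versus CBDC interaction estimate with its confidence interval for each of the six factors and each primary outcome, alongside the 99% subgroup intervals already planned.
2. Do not interpret a non-significant interaction as evidence of equal effects across subgroups.

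The cost is wording in two sections of each document and a few more intervals from models already planned. The stated power for heterogeneity becomes less favourable. The primary-outcome database is already frozen (SAP section 8), so the practical gain is in how the results are interpreted.
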